#### 5.8.4.2. Guidelines for Hand-foot Skin Reactions (HFSR)

Episodes of Hand-foot Skin Reaction (HFSR) have been observed in subjects receiving dabrafenib and other combination studies of dabrafenib and trametinib. Guidelines for management of HFSR are based on experience with other kinase inhibitors [[Lacouture, 2008](#); [McLellan, 2011](#)].

Measures for PPES should include:

- Lifestyle modification:** avoidance of hot water, traumatic activity, constrictive footwear, or excessive friction on the skin and the use of thick cotton socks and gloves, and shoes with padded insoles
- Symptomatic treatments:** apply moisturizing creams frequently, topical keratolytics (e.g. urea 20-40 % cream, salicylic acid 6%, tazarotene 0.1% cream, fluorouracil 5%

cream), clobetasol propionate 0.05% ointment for erythematous areas, topical lidocaine 2%, and / or systemic pain medication such as nonsteroidal anti-inflammatory drugs, codeine, and pregabalin for pain.

- Dose modification may also be required.

#### **5.8.4.3. Guidelines for cuSCC and treatment emergent melanomas**

**Cutaneous squamous cell carcinomas and keratoacanthomas (KA)** have been observed in subjects treated with dabrafenib and the combination of dabrafenib and trametinib (see dabrafenib and trametinib combination IB); [GlaxoSmithKline Document Number [2011N126811\\_00](#).2012]. These treatment-related cuSCC should be surgically removed according to institutional practice. Dose modifications or interruptions of the study treatment are not required for cuSCC. Occurrence of cuSCC must be reported as an SAE. Pathology report should be placed in subject chart.

**New Primary Melanoma:** New primary melanomas have been reported in patients treated with dabrafenib. These were identified primarily within the first 5 months of therapy and did not require treatment modification other than excision. Monitoring for skin lesions should occur as described for cuSCC.

New primary cancers and treatment-emergent malignancies, with the exception of basal cell carcinoma (BCC) should be reported as a SAE. BCC should be reported as an AE or SAE based on the discretion of the investigator. A biopsy of the new malignancy should be taken, where possible, and results submitted to Novartis for further analyses. Testing of these biopsies may include RAS mutation testing and analysis of proteins related to the action of dabrafenib. Genomic alterations, which include but not limited to DNA, RNA and protein analysis of these biopsy specimens may be performed, and would be restricted to the analysis of pathway mutations known to be associated with, and relevant to, BRAF-mutant tumors or pathway activation.

Evaluate for symptoms or clinical signs of non-cutaneous, new primary/recurrent malignancies before initiation of treatment, periodically during treatment, or as clinically indicated. Following discontinuation of study treatment, monitoring for non-cutaneous secondary/recurrent malignancies should continue for up to 6 months or until initiation of another anti-neoplastic therapy. Abnormal findings should be managed according to clinical practices.

#### **5.8.5. Guidelines for Other Adverse Events of Special Interest on the dabrafenib and trametinib combination treatment arm**

##### **5.8.5.1. Guidelines for Pyrexia**

Episodes of pyrexia have been observed in subjects receiving dabrafenib monotherapy, and is increased in incidence and severity in subjects receiving dabrafenib in combination with trametinib (see dabrafenib and dabrafenib and trametinib combination IBs); [GlaxoSmithKline Document Number [CM2010/00010/02](#) 2011 and GlaxoSmithKline Document Number [2011N126811\\_00](#).2012]. In a minority of cases the pyrexia was accompanied by symptoms such as severe chills, dehydration, hypotension, dizziness or

weakness.

Subjects should be instructed on the importance of immediately reporting febrile episodes. In the event of a fever, the subject should be instructed to take anti-pyretics (e.g. ibuprofen or acetaminophen/paracetamol) as appropriate to control fever. The use of oral corticosteroids should be considered in those instances in which anti-pyretics are insufficient. Monitor serum creatinine and other evidence of renal function during and following severe events of pyrexia (see Section 5.8.5.3).

Guidelines regarding management and dose modifications for pyrexia considered to be related to study treatment are provided in [Table 11](#)

**Table 11 Management and Dose Modification Guidelines for Pyrexiaa, b**

Adverse Event	Adverse Event Management	Action and Dose Modification
Pyrexia a	
All Eventsb:
 
 
• Clinical evaluation for infection and hypersensitivityc
 
• Laboratory work-upc
 
• Hydration as requiredd
 
 
1st Eventb:
 
 
• Administer anti-pyretic treatment as clinically indicated and initiate prophylactic treatment if associated with rigors, renal failure, dehydration or hypotensione
 
 
2nd Eventf
 
 
• Within 3 days of onset of pyrexia               
 
○ Optimize anti-pyretic therapy
 
○ Consider oral corticosteroids (i.e., prednisone 10 mg) for at least 5 days or as clinically indicatedf
 
 
 
	
1st Event:
 
 
• Interrupt dabrafenib
 
• Continue trametinib
 
• Once pyrexia resolves to baseline, restart dabrafenib at the same dose level               
 
○ If fever was associated with rigors, renal failure, dehydration or hypotension, reduce dabrafenib by one dose levelg
 
 
 
 
2nd Event:
 
 
• Interrupt dabrafenib
 
• Continue trametinib
 
• Once pyrexia resolves to baseline, restart dabrafenib at the same dose level               
 
○ If fever was associated with rigors, renal failure, dehydration or hypotension, reduce dabrafenib by one dose levelg
 
 
 

Adverse Event	Adverse Event Management	Action and Dose Modification
	
Subsequent Events:
 
 
• Within 3 days of onset of pyrexia:               
 
○ Optimize oral corticosteroid dose as clinically indicated for recalcitrant pyrexiaf
 
○ If corticosteroids have been tapered and pyrexia recurs, restart steroids
 
○ If corticosteroids cannot be tapered consult Global Clinical Lead
 
 
 
	
Subsequent Events:
 
 
• Interrupt dabrafenib
 
• Continue trametinib
 
• Once pyrexia resolves to baseline, restart dabrafenib reduced by one dose levelg
 
• If dabrafenib must be reduced to <75mg BID, permanently discontinue dabrafenib. Trametinib may be continued.
 

- a. Pyrexia is defined as a body temperature equal to or above 38.5 Celsius or 101.3°Fahrenheit.
- b. For subjects experiencing pyrexia complicated by rigors, severe chills, etc., a clinical evaluation and laboratory work-up is mandatory for each event; anti-pyretic treatment should be started immediately at the first occurrence and prophylactic anti-pyretic treatment is recommended
- c. Thorough clinical examination for signs and symptoms of infection or hypersensitivity is required; laboratory work-up should include full-blood-count, electrolytes, creatinine, blood urea nitrogen (BUN), C-reactive protein (CRP), liver-function tests, blood culture, and urine culture.
- d. Oral hydration should be encouraged in subjects without evidence of dehydration. Intravenous hydration is recommended in subjects experiencing pyrexia complicated by dehydration/hypotension.
- e. Anti-pyretic treatment may include acetaminophen, ibuprofen, or suitable anti-pyretic medication according to institutional standards. Prophylactic anti-pyretic treatment may be discontinued after three days in the absence of pyrexia.
- f. In subject experiencing pyrexia complicated by rigors, severe chills, etc., which cannot be controlled with anti-pyretic medication, oral corticosteroids should be started at the 2nd event and doses should be gradually increased for subsequent events.
- g. Dabrafenib should be reduced by one dose level after three episodes of pyrexia complicated by rigors, severe chills, etc., which cannot be managed by best supportive care and increasing doses of oral steroids. Escalation of dabrafenib is allowed if no episode of pyrexia is observed in the 4 weeks subsequent to dose reduction.

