**Table 4 Dose Level Reduction Guidelines**

Dose Level	Dabrafenib Dose/Schedule	Trametinib Dose/Schedule
Starting Dose	150 mg BID	2 mg once daily
-1 (1 st Dose reduction)	100 mg BID	1.5 mg once daily
-2 (2 nd Dose reduction)	75 mg BID	1.0 mg once daily

Abbreviation: BID = twice daily

If an AE resolves to grade 1 or baseline at the reduced dose level, and no additional toxicities are seen after 4 weeks of study treatment at the reduced dose, the dose may be increased to the previous dose level.

If the subject requires both a dose reduction below 75 mg BID for dabrafenib and a dose reduction below 1 mg once daily for trametinib, the subject must discontinue the combination study treatment.

If a dose reduction below 75 mg BID for dabrafenib is required, dabrafenib will be permanently discontinued but these subjects will be allowed to continue trametinib. If a dose reduction below 1.0 mg once daily for trametinib is required, then trametinib will be permanently discontinued, but these subjects will be allowed to continue dabrafenib.

**Note: Approval from the Novartis Global Clinical Lead is required to restart study treatment after  $\geq 21$  days of interruption.**

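### Table 11 and its own footnote g give different triggers for reducing dabrafenib after complicated pyrexia, and the protocol does not say which governs

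*Protocol*

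**What the plan says.** Protocol section 5.8.5.1 sends the reader to Table 11 for managing treatment-related pyrexia. The table has an action for each event number.

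- **1st and 2nd event.** The wording is the same in both cells. Dabrafenib is interrupted, and the default is: "Once pyrexia resolves to baseline, restart dabrafenib at the same dose level". An exception follows: "If fever was associated with rigors, renal failure, dehydration or hypotension", then "reduce dabrafenib by one dose level g". The final letter is the footnote marker, and it sits on the reduction itself in both cells.
- **Subsequent events.** Dabrafenib is interrupted and then restarted "reduced by one dose level g". The same marker appears, and the cell does not ask whether the fever was complicated or how it responded to treatment.
- **Footnote g.** "Dabrafenib should be reduced by one dose level after three episodes of pyrexia complicated by rigors" or similar symptoms such as severe chills, with the further condition that these are episodes "which cannot be managed by best supportive care and increasing doses of oral steroids". A second sentence allows re-escalation after four weeks without pyrexia.

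Section 5.8.1 (Table 4) sets the dabrafenib levels at 150, 100 and 75 mg BID, with this floor: "If a dose reduction below 75 mg BID for dabrafenib is required, dabrafenib will be permanently discontinued".

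**The concern.** A footnote normally explains or limits the action it is attached to. Here it gives that action another threshold: three episodes instead of one, plus a failure-of-treatment condition that the cells lack. An investigator facing a first fever with rigors finds one instruction in the cell and another in the note that the cell cites. Nothing in section 5.8.5.1 or Table 11 ranks the two.

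The main stake is that patients with the same history could receive different doses, or could stop or stay on dabrafenib, depending on which text the site followed. The second stake is reporting. The SAP summarises dose reductions by number and reason, average daily dose (section 12.1) and adverse events leading to reductions (section 12.5), and it lists pyrexia as an event of special interest (section 12.3). Those outputs could mix two rules without showing it.

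**Working it through.** There is no statistical figure to reproduce. The check compares the two texts and then counts dose steps with the protocol's own levels.

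**1. The triggers side by side**

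| | 1st and 2nd event cells | Subsequent events cell | Footnote g |
|---|---|---|---|
| Action | one level down, marked g | one level down, marked g | one level down |
| Episodes needed | one | third or later event, complicated or not | three complicated |
| Complications named | rigors, renal failure, dehydration, hypotension | none required | rigors, severe chills and an open-ended remainder |
| Failure of supportive care and steroids | not required | not required | required |

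**2. Where they collide.** Rigors is the only complication that both lists name, so a first or second fever with rigors falls under both texts. For renal failure, dehydration or hypotension without rigors, the overlap depends on how far the open-ended wording in footnote g reaches. For an uncomplicated first or second event there is no conflict: the cell says restart at the same level, and footnote g does not apply.

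**3. Dose paths.** Take a patient who starts at 150 mg BID and has three successive fevers with rigors and no re-escalation.

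| After event | Following the cells | Following footnote g |
|---|---|---|
| 1 | 100 mg BID | 150 mg BID |
| 2 | 75 mg BID | 150 mg BID |
| 3 | next step is below 75 mg BID: permanently stopped | 100 mg BID if the episodes were refractory; otherwise g calls for no reduction |

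The paths differ from the first event and end in discontinuation against at most one reduction.

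**4. The subsequent events row.** Three uncomplicated fevers give 150, 150 and then 100 mg BID under the cells. Footnote g, although marked on that third-event reduction, calls for none.

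**5. How many patients.** Protocol section 1.1.3.2 reports pyrexia in 52% of Part B subjects, and treatment-related pyrexia in 58% of the 79 at the study dose. Assume those rates carry over to the roughly 120 planned subjects. Then 0.52 × 120 ≈ 62 to 0.58 × 120 ≈ 70 would have pyrexia of any kind. Section 5.8.5.1 says accompanying symptoms such as severe chills, dehydration or hypotension occurred in a minority of cases. No rate of complicated pyrexia is given, so the number exposed to the conflict at events 1 and 2 lies somewhere below 62 to 70 and cannot be fixed from the documents.

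**The case against.** The best defence is that footnote g does not say a reduction may come *only* after three episodes. Reducing at a complicated first event breaks no word of it, so g could be an extra trigger for recalcitrant cases. A second defence is that the marker is there for the re-escalation sentence. Table 10 footnote c and Table 12 footnote d attach re-escalation notes to reductions in just this way.

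Part of this stands. The footnote contains no explicit prohibition, and the re-escalation sentence may explain why the marker appears in all three rows. It does not remove the problem. The first sentence of the footnote still states a different threshold for the very action it annotates, and sites would have to know to disregard it. As an extra trigger it would have little work to do, because under the cells a patient with rigors has been reduced before a third episode occurs.

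An appeal to clinical judgment is weaker. That language in section 5.8.2 accompanies the general guidelines for events without specific rules, and pyrexia has its own table.

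Two objections on scale do stand. The affected displays are descriptive. The trial was also late in its course: the amendment rationale records 9 patients still on treatment and expects the last visit around October 2017, and the SAP is dated 5 March 2018. A letter to sites could reach few treated patients.

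**Conclusion.** The inconsistency is real on the current text. For a fever with rigors, Table 11 and footnote g give different triggers for the same reduction, and the subsequent events row does not match the footnote either. On the stated three-event path the difference is permanent discontinuation against at most one step down, assuming successive rigor-complicated fevers and no re-escalation.

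Three stronger readings are not supported:

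- **That the conflict covers the trial's commonest toxicity as a whole.** The 52% and 58% figures count all pyrexia, while the conflict at events 1 and 2 is confined to complicated pyrexia.
- **That every complicated event is caught by both texts.** The complication lists overlap expressly only on rigors.
- **That the primary result is at risk.** The Cohort A test counts confirmed intracranial responders against a fixed threshold and uses no dose-reduction or exposure data.

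The point concerns patient dosing and how the descriptive dose-reduction and exposure summaries are read.

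**What to change.** 1. Reconcile the three Table 11 cells (1st, 2nd and subsequent events) with footnote g so that one rule applies to each event. Which rule is a clinical decision for the sponsor; this review takes no position on it.
2. Tell sites which text governs for patients still on treatment.
3. State in the clinical study report how pyrexia-related dabrafenib reductions were actually applied. The planned listings of dabrafenib dose reductions (23.0020) and of pyrexia (23.0215) could be read together to see at which event number patients were reduced. Whether the complicating features can be identified depends on what was recorded.

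The cost is one clarification letter or amendment line, plus a short statement in the report. Given the trial's stage, the report statement is likely to matter most.

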#### 5.8.5.2. Guidelines for Diarrhea

Episodes of diarrhea have occurred in subjects receiving dabrafenib, trametinib, or both therapies in combination. Other, frequent causes for diarrhea including concomitant medications (e.g., stool softeners, laxatives, antacids, etc.), infections by *C. difficile* or other pathogens, partial bowel obstruction, etc., should be clinically excluded.

Guidelines regarding management and dose reduction for diarrhea considered to be related to study treatment by the investigator are provided in [Table 12](#).

**Table 12 Management and Dose Modification Guidelines for Diarrhea**

CTCAE Grade	Adverse Event Management	Action and Dose Modification
Uncomplicated Diarrhea a  Grade 1 or 2	
 
Diet: stop all lactose containing products; eat small meals, BRAT-diet (banana, rice, apples, toast) recommended.
 
Hydration: 8-10 large glasses of clear liquids per day (e.g., Gatorade or broth).
 
Loperamidec: initially 4 mg, followed by 2 mg every four hours or after every unformed stool; maximum 16 mg/day. Continue until diarrhea free for 12 hours.
 
Diarrhea ≥ 24h: loperamide 2 mg every two hours; maximum 16 mg/day. Consider adding oral antibiotics.
 
Diarrhea ≥ 48h: loperamide 2 mg every two hours; maximum 16 mg/day. Add budesonide or other second-line therapies (otretotide, or tincture of opium) and oral antibiotics.
 
	
 
Continue study treatment.
 
If diarrhea is grade 2 for ≥ 48h, interrupt study treatment until diarrhea resolves to grade ≤1.
 
Restart study treatment at the same dose level
 

Uncomplicated Diarrhea a  Grade 3 or 4 Any Complicated Diarrhea b	
 
Clinical evaluation mandatory.
 
Loperamidec: initially 4 mg, followed by 2 mg every four hours or after every unformed stool; maximum 16 mg/day. Continue until diarrhea free for 12 hours
 
Oral antibiotics and second-line therapies if clinically indicated.
 
Hydration: intravenous fluids if clinically indicated.
 
Antibiotics (oral or intravenous) if clinically indicated.
 
Intervention should be continued until the subject is diarrhea free for ≥ 24 hours.
 
Intervention may require hospitalization for subjects at risk of life-threatening complications
 
	
 
Interrupt study treatment until diarrhea resolves to grade ≤1.
 
Restart with study treatment reduced by one dose leveld.
 
If 3 dose reductions of study treatment are clinically indicated, permanently discontinue study treatment.
 

CTCAE = Common Terminology Criteria for Adverse Events

- Uncomplicated diarrhea** defined by the absence of symptoms such as, cramping, nausea/vomiting ≥ grade 2, decreased performance status, pyrexia, sepsis, neutropenia grade ≥3, frank bleeding, and/or dehydration requiring intravenous fluid substitution
- Complicated diarrhea** defined by the presence of symptoms such as, cramping, nausea/vomiting ≥ grade 2, decreased performance status, pyrexia, sepsis, neutropenia grade ≥3, frank bleeding, and/or dehydration requiring intravenous fluid substitution
- Loperamide should be made available prior to start of study treatment so loperamide administration can begin at the first signs of diarrhea
- Escalation of study treatment to previous dose level is allowed after consultation with the Global Clinical Lead and in the absence of another episode of complicated or severe diarrhea in the 4 weeks subsequent to dose reduction

### 5.8.5.3. Guidelines for Renal Insufficiency

Cases of renal insufficiency have occurred in subjects receiving dabrafenib and the combination of dabrafenib and trametinib. Prior to start of study treatment, concomitant

medications should be reviewed for the potential risk of inducing nephrotoxicity and concomitant medications should be modified if clinically possible.

Guidelines regarding management and dose reduction for renal insufficiency considered to be related to study treatment by the investigator are provided in [Table 13](#).

Table 13 Management and Dose Modification Guidelines for Renal Insufficiency

Serum Creatinine Level	Adverse Event Management	Action and Dose Modification
Serum creatinine increase >0.2 mg/dL (18 umol/L) but ≤0.5 mg/dL (44 umol/L) above baseline	
 
• Recheck serum creatinine within 1 week
 
• Serum creatinine increase > 1 week: contact Novartis Global Clinical Lead. If elevation persists beyond 4 weeks, recommend evaluation (consider renal biopsy) for etiology; consider nephrology consultation.
 
• If pyrexia is present, treat pyrexia as per guidelinesa.
 
	
 
• Continue study treatment at the same dose level.
 

Serum creatinine increase >0.5 mg/dL (44 umol/L) above baseline or serum creatinine >2 mg/dL (> 177 umol/L)	
 
• Monitor serum creatinine ≥ 2- times per week.
 
• Hospitalization may be necessary if serum creatinine cannot be monitored frequently.
 
• If pyrexia is present, treat pyrexia per guidelinesa.
 
• Consult nephrologist if clinically indicated.
 
• Perform renal biopsy if clinically indicated, for example:               
 
○ Renal insufficiency persists despite volume repletion.
 
○ Subject has new rash or signs of hypersensitivity (such as elevated eosinophil count)
 
 
 
	
 
• Interrupt study treatment until serum creatinine recovers to baseline.
 
• Restart with study treatmentb
 

NSAIDS = non-steroidal anti-inflammatory drugs

- a. NSAIDs can induce renal insufficiency, especially in subjects with dehydration; encourage oral fluids or consider intravenous fluids as clinically indicated. See guidelines for pyrexia Section [5.8.5.1](#).
- b. Investigator may restart at either the same or a reduced dose level. Escalation of study treatment to previous dose level is allowed if another episode of renal insufficiency does not occur after 4 weeks of dose reduction. Consultation with Novartis Global Clinical Lead is required before restarting study treatment if there is evidence of thrombotic microangiopathy.

#### 5.8.5.4. Guidelines for Visual Changes

Episodes of visual changes have been observed in subjects receiving trametinib, dabrafenib, and combination therapy. An ophthalmologist should be consulted if changes in vision develop [Refer to Section [7.4.5](#)]. However, if the visual changes are clearly unrelated to study treatment (e.g., allergic conjunctivitis), then monitor closely as it may be reasonable to defer ophthalmic examination.

Treatment with dabrafenib has been associated with the development of uveitis, including iritis. Monitor patients for visual signs and symptoms (such as, change in vision, photophobia and eye pain) during therapy. Special attention should be given to retinal findings [e.g., retinal pigment epithelial detachment (RPED) or retinovascular abnormalities (i.e., branch or central retinal vein occlusions (RVO)]. For events of visual changes (regardless of severity) for which an ophthalmic examination is conducted, a blood sample for PK analysis must be drawn as close as possible to the time of the event.

Guidelines regarding management and dose reduction for visual changes and/or ophthalmic examination findings considered to be related to study treatment are provided in [Table 14](#).

